2.2. Trial Objectives

2.2.1. Primary Objective(s)

⇒ Phase I

The primary objective of phase I is to establish the safety of hu3F8-BsAb and determine the MTD and the RP2D.

⇒ Phase II

The primary objectives of phase II are:

- In Group 1: Assess the Overall Response Rates (ORR) of hu3F8-BsAb in patients with relapsed or refractory NB
- In Group 2: Assess the PFS in patients with relapsed or refractory osteosarcoma at 4 months from the first hu3F8-Bsab treatment.

2.2.2. Secondary Objective(s)

⇒ Phase I

The secondary objectives are:

- To study the PK of hu3F8-BsAb.
- To evaluate HAHA.
- To assess the anti-tumor activity and overall response rates of hu3F8-BsAb in patients with relapsed or refractory NB, osteosarcoma and other GD2(+) tumors.
- ⇒ Phase II

The secondary objectives are:

- To evaluate the duration of complete remission in groups 1 and 2.
- In Group 2: Assess the overall response rates of hu3F8-BsAb in patients with relapsed or refractory osteosarcoma.
- To continue to assess the safety/toxicity of hu3F8-BsAb.
- To evaluate HAHA.

2.2.3. Exploratory Objective(s)

⇒ Phase I

The exploratory objectives are:

- To study immunological effects of hu3F8-BsAb
- To study the effects of hu3F8-BsAb on BM Ribonucleic Acid (RNA)

- To study the effects of stool microbiome of the activity of hu3F8-BsAb.

⇒ Phase II

The exploratory objectives are:

- To assess Overall Survival (OS) and PFS after treatment with hu3F8-BsAb.
- To study immunological effects of hu3F8-BsAb
- To study the effects of hu3F8-BsAb on BM Deoxyribonucleic Acid (DNA) and RNA (Neuroblastoma patients only).
- To study the effects of stool microbiome of the activity of hu3F8-BsAb.

2.3. Sample Size and Power

2.3.1. Phase I

Phase I will enroll up to 30 evaluable patients. 10-15 patients/year are expected to be enrolled, and it is expected that the trial will be open to accrual for 36 months. All patients who are enrolled in the trial and receive at least one dose of hu3F8-BsAb are considered evaluable for toxicity. Additional patients will be enrolled to replace any patients who are enrolled, but do not receive any treatment. An amendment in the dose levels was done after the inclusion of 5 patients to dose levels 1 to 4; however, the modifications only impacted dose level 5 and higher, therefore the 5 first patients are still part of the CRM and will be analyzed as planned. The amendment does not modify the operating characteristics of the CRM.

2.3.2. Phase II

2.3.2.1. For Group 1 (relapsed or refractory NB)

The null hypothesis is that the hu3F8-BsAb treatment has ORR < 25% (assumption based on results of previous clinical trials / see protocol section 14.2.1.1). The alternative hypothesis is that the ORR after the hu3F8-BsAb treatment is \geq 25%. The power is calculated assuming ORR=50%.

30 patients will be recruited. As pre-specified in the protocol a 95% one-sided confidence interval (CI) (corresponding to a two-sided 90% CI) for ORR will be computed using Wilson's method. If the confidence interval does not include the null ORR rate of 25% this treatment will be considered as successful. The sample size is based on confidence interval half-width 0.15 and desirable ORR rate of 50%. Based on simulation if the true rate is 50% the CI will not include 25% with probability 90%. In addition to 90% CI, 95% CI will also be presented.

Patients from the Full Analysis Set (FAS) (see section 4.3 for the definition) will be included into the assessment even if they are removed from the trial before completing cycle 4 due to any reasons. 10-15 patients/year are expected to be enrolled, therefore accrual of this group will be completed in 2-3 years.

2.3.2.2. For Group 2 (relapsed or refractory osteosarcoma)

The null hypothesis is that the hu3F8-BsAb treatment has 4-month PFS <12% (assumption based on results of seven clinical trials / see protocol section 14.2.1.2). The alternative hypothesis is that the 4-month PFS after hu3F8-BsAb treatment is \geq 12%, whereas the power is calculated assuming that the 4-month PFS after hu3F8-BsAb treatment is 40%. 18 patients will be accrued.

According to the protocol, a 95% one-sided confidence (corresponding to a two-sided 90% CI) interval for 4 months PFS will be computed using Wilson's method. If the confidence interval does not include the null rate of 12%, this treatment will be considered as successful. The sample size is based on confidence interval half-width 0.190 and desirable 4 months PFS rate of 40%. Based on simulation if the true rate is 40% the CI will not include 12% with probability 90%.

5-10 patients/year are expected to be enrolled, therefore accrual of this group will be completed in 2-4 years.

Patients from the FAS (see section 4.3 for the definition) will be included. In order to take censoring prior to 4 months into account the CIs will be calculated using Kaplan-Meier methods rather than Wilsons's method. This is a change to the protocol and has been described in section 7 below. In addition to 90% CI, 95% CI will also be presented.

2.4. Primary Variable(s)

2.4.1. Phase I

The primary endpoint will be the occurrence of DLT during cycle 1. Based on this, the MTD and the RP2D will be determined.

2.4.2. Phase II

2.4.2.1. ORR For Group 1 (relapsed or refractory NB)

For relapsed or refractory NB patients, the primary endpoint will be the ORR defined as the proportion of patients achieving CR or PR based on INRC as the best response at the end of cycle 4.

For this analysis, Best Overall Response (BOR) will be derived as the best response at the end of cycle 4, excluding any potential response assessments after initiation of any new prohibited anticancer treatment.

Overall response will be defined by the investigator in the Response Summary eCRF form by combining response of the individual components (i.e. soft tissue, bone, and bone marrow disease):

- Complete Response/Remission (CR): All components meet criteria for CR.

- Partial Response/Remission (PR): PR in at least one component and all other components are either CR, Minimal Disease (MD) (bone marrow), PR (soft tissue or bone), or Not Involved (NI)*; no component with progression disease.
- Mixed Response (MR): PR or CR in at least one component but at least one other component with Stable Disease; no component with PD.
- Stable Disease: Stable Disease in one component with no better than Stable Disease or NI* in any other component; no component with progressive disease.
- Progressive Disease: Any component with Progressive Disease.
 *NI Site not involved at trial entry and remains uninvolved.

Mixed Response corresponds to Minor Response in the *Revisions to the International Neuroblastoma Response Criteria: A Consensus Statement From the National Cancer Institute*³. Thus it will be considered as Minor Response for the analyses.

Primary (soft tissue) Tumor Response:

- CR: <10mm residual soft tissue at primary site AND Complete resolution of MIBG or Fluorine-18-Fluorodeoxyglucose Positron Emission Tomography (FDG-PET) uptake (for MIBG-nonavid tumors) at primary site.
- PR: ≥30% decrease in longest diameter of primary site AND MIBG or FDG-PET uptake at primary site stable, improved, or resolved.
- Progressive Disease: >20% increase in longest diameter taking as reference the smallest sum on trial (this includes the baseline sum if that is the smallest on trial) AND Minimum absolute increase of 5mm in longest dimension.
- Stable Disease: Neither sufficient shrinkage for PR or sufficient increase for PD at the primary site.

Tumor Response at Metastatic Soft Tissue and Bone Sites:

- CR: Resolution of all sites of disease, defined as: Nonprimary target and nontarget lesions measure <10mm AND Lymph nodes identified as target lesions decrease to a short axis <10mm AND MIBG uptake or FDG-PET uptake (for MIBG-nonavid tumors) of nonprimary lesions resolves completely.
- PR: ≥30% decrease in sum of diameters of nonprimary target lesions compared with baseline AND all of the following:
 Nontarget lesions may be stable or smaller in size AND No new lesions AND ≥50% reduction in MIBG absolute bone score (relative MIBG bone score ≥ 0.1 to ≤ 0.5) or ≥50% reduction in number of FDG-PET-avid bone lesion
- Progressive Disease: Any of the following: Any new soft tissue lesion detected by CT/MRI that is also MIBG avid or FDG-PET avid Any new soft tissue lesion seen on anatomic imaging that is biopsied and confirmed

to be neuroblastoma or ganglioneuroblastoma Any new bone site that is MIBG avid A new bone site that is FDG-PET avid (for MIBG-nonavig tumors) AND has CT/MRI findings consistent with tumor OR has been conferment histologically to be neuroblastoma or ganglioneuroblastoma

>20% increase in longest diameter taking as reference the smallest sum on trial (this includes the baseline sum if that is the smallest on trial) AND minimum absolute increase of 5mm in sum diameters of target soft tissue lesions Relative MIBG score >1.2

- Stable Disease: Neither sufficient shrinkage for PR or sufficient increase for PD of non primary lesions

Bone Marrow Metastatic Response:

- CR: Bone marrow with no tumor infiltration on reassessment, independent of baseline tumor involvement.
- Progressive Disease: Any of the following: Bone marrow without tumor infiltration that becomes >5% tumor infiltration on reassessment OR Bone marrow with rumor infiltration that increases by > two-fold and has >20% tumor infiltration on reassessment.
- MD: Any of the following: Bone marrow with ≤5% tumor infiltration and remains >0 to ≤5% tumor infiltration on reassessment OR Bone marrow with no tumor infiltration that has ≤5% tumor infiltration on reassessment OR Bone marrow with >20% tumor infiltration that has >0 to ≤5% tumor infiltration on reassessment
- Stable Disease: Bone marrow with tumor infiltration that remains positive with >5% tumor infiltration on reassessment but does not meet CR, MD, or Progressive Disease criteria.

2.4.2.2. 4-month PFS for Group 2 (relapsed or refractory osteosarcoma)

For relapsed or refractory osteosarcoma patients, the primary endpoint is the 4-month PFS. PFS is defined at the time from first dose of treatment to the date of first progression or death from any cause, whichever occurs first.

The assessment of progression will be done based on response criteria assessed from tumor assessments. Patients without progression or death at time of analysis will be censored at the date of their last evaluable response assessment based on Response Evaluation Criteria in Solid Tumors version 1.1 (RECIST v1.1)⁴ assessment.

PFS will be censored on the date of the last adequately evaluable tumor assessment:

- for patients who do not have an event (progression or death),
- for patients who start new anti-cancer treatment prior to an event,
- for patients with an event after a time period without assessments of response corresponding to at least two consecutive missing response assessments.

Patients who do not have a baseline tumor assessment or who do not have any post-baseline tumor assessments will be censored on the date of the first treatment unless death occurred on or before the time of the second planned tumor assessment (Cycle 4 scan), in which case the death will be considered an event.

PFS (in months) will be computed as [date of event or censoring – first dose of treatment + 1]/30.4375.

PFS will be calculated with one decimal.

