Nontarget lesions may be stable or smaller in size AND No new lesions AND \geq 50% reduction in MIBG absolute bone score (relative MIBG bone score \geq 0.1 to \leq 0.5) or \geq 50% reduction in number of FDG-PET-avid bone lesion

• PD: Any of the following:

Any new soft tissue lesion detected by CT/MRI that is also MIBG avid or FDG-PET avid

Any new soft tissue lesion seen on anatomic imaging that is biopsied and confirmed to be neuroblastoma or ganglioneuroblastoma

Any new bone site that is MIBG avid

A new bone site that is FDG-PET avif (for MIBG-nonavig tumors) AND has CT/MRI findings consistent with tumor OR has been conferment histologically to be neuroblastoma or ganglioneuroblastoma

>20% increase in longest diameter taking as reference the smallest sum on study (this includes the baseline sum if that is the smallest on study) AND minimum absolute increase of 5mm in sum diameters of target soft tissue lesions

Relative MIBG score ≥ 1.2

- SD: Neither sufficient shrinkage for PR or sufficient increase for PD of nonprimary lesions.
- **12.3.4** Bone Marrow Metastatic Response:
 - CR: Bone marrow with no tumor infiltration on reassessment, independent of baseline tumor involvement.
 - PD: Any of the following:

Bone marrow without tumor infiltration that becomes >5% tumor infiltration on reassessment OR

- Bone marrow with rumor infiltration that increases by > two-fold and has >20% tumor infiltration on reassessment.
- MD: Any of the following:

Bone marrow with \leq 5% tumor infiltration and remains >0 to \leq 5% tumor infiltration on reassessment OR

Bone marrow with no tumor infiltration that has \leq 5% tumor infiltration on reassessment OR

Bone marrow with >20% tumor infiltration that has >0 to \leq 5% tumor infiltration on reassessment

- SD: Bone marrow with tumor infiltration that remains positive with >5% tumor infiltration on reassessment but does not meet CR, MD, or PD criteria.
- **12.4** Disease response for non-neuroblastoma tumors will use the Response Evaluation Criteria in Solid Tumor (RECIST) Version 1.1.
- **12.4.1** Measurable Disease:

The presence of at least one lesion that can be accurately measure in at least one dimension with the longest diameter at least 20 mm or lesions at least 10 mm on spiral scan is considered measurable disease.

- **12.4.2** Response Criteria
 - Complete Response (CR): Disappearance of all clinical and radiological evidence of target lesions.

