6.6.1. Primary Efficacy Analysis for Phase II

6.6.1.1. ORR for Group 1

The primary efficacy variable of relapsed or refractory NB patients of phase II is defined as ORR at the end of cycle 4 excluding potential response assessments after initiation of any new prohibited anticancer treatment.

The null hypothesis is that the hu3F8-BsAb treatment has ORR < 25%. The alternative hypothesis is that the ORR after the hu3F8-BsAb treatment is \geq 25%.

90% and 95% two-sided confidence intervals for ORR will be computed using Wilson's method. If the two-sided 90% confidence interval does not include the null ORR rate of 25% the treatment will be considered as successful.

Patients in the FAS will be included into the assessment even if they are removed from the trial before completing cycle 4 due to any reasons.

The number and percentage of responder patients (Yes/ No) with details by best response categories (CR, PR and MR versus Stable Disease, Progressive Disease, Not Evaluable, Missing) will be described in the FAS and the confidence interval using the Wilson's method will be provided.

In addition, overall responses at each cycle will excluding potential response assessments after initiation of any new prohibited anticancer treatment be provided with the 90% and 95% confidence intervals using the Wilson's method.

Patients whose CRF response is "Very Good Partial Response" will be considered as "Partial Response" for the analyses.

ORR values will be also presented in a data listing as well as overall responses at each cycle.

6.6.1.2. 4-month PFS for Group 2

The primary efficacy variable of relapsed or refractory osteosarcoma patients of phase II is defined as 4-month PFS.

The null hypothesis is that the hu3F8-BsAb treatment has 4-month PFS <12%. The alternative

hypothesis is that the 4-month PFS after hu3F8-BsAb treatment is $\geq 12\%$.

The Kaplan-Meier estimate of the median time will be provided with 25th percentile and 75th percentile as well as PFS rates at 4 months with corresponding 90% and 95% Confidence Intervals.

In addition, the results will be presented graphically in Kaplan-Meier plots including count for numbers of patients at risk.

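### The metastatic PR rule contradicts itself for relative MIBG bone scores above 0 and below 0.1, so Group 1 ORR could be understated if its bracket is applied literally

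*SAP*

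**What the plan says.** The Group 1 primary endpoint is the proportion with CR or PR under the revised INRC. Both documents give the same component rules for metastatic soft tissue and bone (Protocol 12.3.3; SAP 2.4.2.1).

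- **PR** needs, among other conditions, a fall of at least 50% in bone uptake. In the SAP this reads "reduction in MIBG absolute bone score (relative MIBG bone score ≥ 0.1 to ≤ 0.5". The Protocol has the same wording, "reduction in MIBG absolute bone score (relative MIBG bone score", with the same limits. A halving of the number of FDG-PET-avid bone lesions is an alternative.
- **CR** needs, among other things, that "MIBG uptake or FDG-PET uptake (for MIBG-nonavid tumors) of nonprimary lesions resolves completely".
- **SD** is the leftover class: "Stable Disease: Neither sufficient shrinkage for PR or sufficient increase for PD of non primary lesions".

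Three further provisions bear on how a patient is finally counted.

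- SAP 2.4.2.1: "Overall response will be defined by the investigator in the Response Summary eCRF form by combining response of the individual components".
- SAP 6.6.1.1: "Patients whose CRF response is 'Very Good Partial Response' will be considered as 'Partial Response' for the analyses".
- SAP 6.6.1.1, responder table: "details by best response categories (CR, PR and MR versus Stable Disease, Progressive Disease, Not Evaluable, Missing".

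Protocol 4.1.2 and 14.2.1.1 and SAP 2.1.2 take the best of the cycle 2 and cycle 4 responses. SAP 2.4.2.1 names only the end of cycle 4.

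**The concern.** The relative score is the follow-up score divided by the baseline score, so a fall of at least 50% is the same as a relative score of 0.5 or less. The bracket restates that with a floor of 0.1. A residual above 0 and below 0.1 therefore meets the leading words, fails the bracket and fails CR. No category names it.

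If the bracket governs, the rule runs backwards: 92% clearance is not PR, while 50% clearance is. A patient with one of the deepest incomplete bone responses could then be a non-responder in a primary endpoint judged against a fixed count. If the leading words govern, the same patient is a PR. Neither document says which applies, and the answer should not be chosen once the patients in question are known.

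**Working it through.** **1. Which scores fall in the gap.** Let R be the relative MIBG bone score.

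| R | Fall of at least 50%? | Inside the bracket? | Complete resolution? | Class |
|---|---|---|---|---|
| 0 | yes | no | yes | CR, if the other CR conditions hold |
| above 0, below 0.1 | yes | no | no | PR by the leading words; not PR by the bracket |
| 0.1 to 0.5 | yes | yes | no | PR, if the other PR conditions hold |
| above 0.5, short of PD | no | no | no | SD |

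For example, R = 0.08 is a 92% fall and lies in the second row; R = 0.5 is a 50% fall and lies in the third.

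**2. What follows for overall response.** Overall PR allows no component at SD. If the bracket makes the metastatic component SD, overall response is at best MR (when another component is CR or PR) and otherwise SD. Neither is CR or PR.

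**3. The plan's own figure.** Inputs: n = 30, null ORR 25%, alternative 50%, success if the two-sided 90% Wilson interval excludes 25% (SAP 2.3.2.1 and 6.6.1.1). With p = x/n and z = 1.645,

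lower limit = [p + z²/(2n) − z·√(p(1−p)/n + z²/(4n²))] / (1 + z²/n).

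- x = 11: lower limit 0.239, so 25% is included.
- x = 12: lower limit 0.267, so 25% is excluded.

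Success therefore needs 12 of 30. P(X ≥ 12 | 30, 0.50) = 0.8998, which reproduces the stated 90%. P(X ≥ 12 | 30, 0.25) = 0.0507.

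**4. What one patient can do.** One reclassified patient moves ORR by 1/30 = 3.3 percentage points. It changes the verdict only if the count would otherwise be exactly 12. At a true ORR of 50% that has probability P(X ≥ 12) − P(X ≥ 13) = 0.8998 − 0.8192 = 0.081.

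**5. What-if range.** Let s be the share of true responders who are in the gap and are finally counted as non-responders. The documents give no value, so s is an assumption. With true ORR 50%, the counted rate is 0.50 × (1 − s):

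| Assumed s | Counted ORR | Probability of at least 12 of 30 |
|---|---|---|
| 0% | 50.0% | 0.900 |
| 2% | 49.0% | 0.879 |
| 5% | 47.5% | 0.843 |
| 10% | 45.0% | 0.767 |
| 20% | 40.0% | 0.569 |

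The first row is as compatible with the documents as any other.

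**6. Who can be affected.** Only patients with MIBG-avid bone disease. If the score takes whole numbers (an assumption; neither document defines the scale), a residual of 1 gives R below 0.1 only from a baseline of 11 upward, since 1/10 = 0.1 and 1/11 = 0.091.

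**The case against.** The strongest reply is that no sensible assessor would call a fall of more than 90% insufficient shrinkage. The SD wording does not clearly capture such a patient, and the leading words of PR do. That is a fair reading, but not the only one: the same section uses the relative score on its own as a PD threshold of 1.2, so a reader may also treat 0.1 to 0.5 as binding.

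A reader might infer that the plan does understate Group 1 ORR. The documents do not support that.

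- The investigator assigns overall response, and nothing shows the bracket being applied by program. The assignment is still made by combining these component criteria, so the ambiguity is passed on.
- Counting very good partial response as PR may rescue these patients. But neither document defines that category or ties it to scores below 0.1, and SAP 6.6.3.5 repeats the sentence for osteosarcoma under RECIST. It leaves the handling open.
- Under best-of-cycles-2-and-4 scoring, a patient who is PR at cycle 2 and in the gap at cycle 4 stays a responder. A patient already in the gap at cycle 2 is not helped, and SAP 2.4.2.1 mentions only cycle 4.
- The FDG-PET branch of PR may catch some patients.
- The direction is not fully certain. A gap patient classed as MR is placed beside CR and PR in the SAP 6.6.1.1 responder table, which conflicts with the CR/PR definition.

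A reader might also try to size the gap by assuming a score scale and a clearance probability. That fails. With whole-number baselines of 11 to 30 and each point clearing independently, a clearance of 0.8 or more is needed before the gap holds a sizeable share, and then at least 99.8% of patients meet the 50% condition, against a design ORR of 50%. At a clearance of 0.5, where 54% meet it, the gap holds 0.06%. The answer is set by the assumption.

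**Conclusion.** The contradiction is certain and appears in both documents: the 50% wording and the bracket disagree for relative scores above 0 and below 0.1, and CR does not take up the difference. Applied literally, the bracket ranks deeper clearance below shallower clearance and could lower Group 1 ORR.

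Whether it would do so, and by how much, cannot be derived. The loss may be zero, and the what-if figures are conditional on an assumed share. The design is untouched: 12 of 30 is still required and the stated 90% power stands. This is a contradictory rule in a primary endpoint that should be settled in advance, not evidence of a biased result.

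**What to change.** Before Group 1 data are read, reconcile the bracket with the 50% condition in Protocol 12.3.3 and SAP 2.4.2.1. State that, for the ORR analysis, a relative MIBG bone score above 0 and below 0.1 counts as PR when the other PR conditions are met. Either of two wordings does this:

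- write the bracket as >0 to ≤0.5; or
- define scores above 0 and below 0.1 as the very good partial response category that SAP 6.6.1.1 already counts as PR.

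If the 0.1 bound comes from the cited INRC publication, record the clarification in SAP section 7. In the same edit, align the place of MR in the SAP 6.6.1.1 table with the CR/PR endpoint.

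The cost is one line in the SAP and the same line in the next protocol amendment. No new data are needed, and the sample size and success rule do not change. The small downside is a documented clarification of a cited criterion.

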4.1.2 Phase II

After RP2D is determined, a phase II study will be carried out to assess the anti-tumor activity of hu3F8-BsAb. Two groups of patients will be studied: Group 1 will consist of patients with relapsed or refractory NB and Group 2 of relapsed or refractory measurable osteosarcoma. Hu3F8-BsAb is given on Days 1 and 8 of each cycle. The duration of each cycle is 28 days. HAHA titer will be measured after each cycle. Extent of disease evaluation (EOD) will be performed after the second dose of cycle 2 and cycle 4, then every 3 months thereafter. A total of 4 cycles will be given, and patients with no life-threatening toxicity clearly attributable to hu3F8-BsAb, no PD, and continuing to meet all eligibility criteria have the option of receiving additional cycles up to 2 years from the start of the hu3F8-BsAb treatment. Patients may continue therapy beyond 4 cycles even if they achieve remission. For Group 1, the overall response rate will be evaluated and is defined as the proportion of patients achieving complete remission (CR) or partial response (PR) based on revised International Neuroblastoma Response Criteria (INRC) as the best response at the end of cycle 2 and cycle 4. (See Section 12). For Group 2, 4-month PFS will be assessed and is defined as the proportion of patients who have not developed PD at the end of 4 months from the first dose of Hu3F8-BsAb. In addition, we will determine the number of patients who have CR or PR as the best response at the end of cycle 2 and cycle 4. (see Section 12)

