14.2.1.2 For Group 2 (relapsed or refractory osteosarcoma)

The objective is to improve 4-month PFS. A retrospective analysis of seven phase II trials conducted by Children's Oncology Group (COG) and its predecessor groups demonstrated that PFS at 4 months from time of enrollment in patients with relapsed measurable disease was 12% (95% CI: 6% to 19%).¹⁹

Our null hypothesis is that the hu3F8-BsAb treatment has 4-month PFS <12% The alternative hypothesis is that the 4-month PFS after hu3F8-BsAb treatment is 40%. We will accrue 18 patients. At the end of the trial 95% one-sided confidence interval for 4 months PFS will be computed using Wilson's method. If the confidence interval does not include the null rate of 12% we will consider this treatment successful. The sample size is based on confidence interval half-width 0.190 and desirable 4 months PFS rate of 40%. Based on simulation if the true rate is 40% the CI will not include 12% with probability 90%.

Patients who received at least 1 dose of hu3F8-BsAb will be included into the assessment even if they are removed from the study before completing cycle 4 due to any reasons. We expect to enroll 5-10 patients/year, therefore accrual of this group will be completed in 2-4 years.

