The overall response will be determined for all protocol specified assessments, ie scheduled assessments (with or without missing information) and also for all unscheduled assessments with non-missing information.

If a scheduled assessment is completely missing (target, non-target, new lesion), the overall response will be NE.

When Stable Disease is believed to be the BOR, it needs to be assessed a minimum of 6 weeks (+/- 7 days) after start of treatment. Otherwise, the BOR will be NE, unless any Progressive Disease was further documented, in which case BOR will be Progressive Disease.

If a patient progressed before this first assessment, he will be considered as 'early progressive'. If this event occurs, the overall response of the patient will be presumed as progression. This corresponds to patient who withdraws without any scan and whose reason for ending treatment or ending study is progressive disease (according to investigator opinion). In case of patient with a reason different to progressive disease, he will not be considered as progressive disease but will be at least considered as non-responder.

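### Group 2 patients who leave with progressive disease before any scan are censored on day 1 for the primary 4-month PFS, which can only raise the estimate

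*SAP*

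**What the plan says.** Protocol 4.1.2 describes the Group 2 endpoint as a simple proportion, "defined as the proportion of patients who have not developed PD at the end of 4 months from the first dose". Protocol 14.2.1.2 adds: "Patients who received at least 1 dose of hu3F8-BsAb will be included into the assessment even if they are removed from the study" before cycle 4, whatever the reason. Success means that a one-sided 95% Wilson interval excludes 12%.

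SAP 2.3.2.2 restates that rule ("a 95% one-sided confidence (corresponding to a two-sided 90% CI) interval for 4 months PFS will be computed using Wilson's method") and then replaces the Wilson interval with Kaplan-Meier limits so that censoring can be handled. SAP 7 discloses the switch.

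SAP 2.4.2.2 sets the censoring. Progression comes from tumor assessments. Patients "who do not have any post-baseline tumor assessments will be censored on the date of the first treatment unless death occurred" no later than the Cycle 4 scan. SAP 5.2.1 refers back to this rule for missing scans. SAP 6.6.1.2 nevertheless says that FAS patients removed before finishing cycle 4 are part of the assessment.

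SAP 2.5.1.3, the Phase I response section, presumes progression for a patient it calls early progressive: "This corresponds to patient who withdraws without any scan and whose reason for ending treatment or ending study is progressive disease". SAP 2.5.1.4 applies the Group 2 censoring rules to Phase I PFS.

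SAP 6.6.2 plans one sensitivity analysis for the primary endpoints, and it concerns Group 1 response. The entries for intercurrent events (6.6.2.3) and missing data (6.6.2.4) are marked not applicable.

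**The concern.** A patient censored on day 1 is in the FAS but never in a risk set when an event occurs. In the 4-month estimate this amounts to deletion. If the patient left because the disease progressed, the reason for deletion is the outcome itself, so the usual assumption that censoring is unrelated to prognosis fails.

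The documents leave room for this to happen. The first scheduled scan follows the second dose of cycle 2, at the earliest day 28 + 8 = 36, and the SAP window is 61 ± 30 days. Protocol 13.1 takes patients off treatment for progression at any time and leaves testing between cycles to clinical judgment.

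The death exception does not fully close the gap. Under Protocol 13.5, patients who stop for progression go off study 30 days after the last dose. That is about day 38 for someone last dosed on day 8, well before the Cycle 4 scan, so a later death may not be recorded.

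At stake is the single-arm success claim for Group 2, where 18 patients are compared with a historical 12% and each patient counts.

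**Working it through.** **Inputs.** Sample size ("18 patients will be accrued"), null rate 12%, design rate 40% and one-sided 5% level are all from SAP 2.3.2.2. The share q of patients who leave unscanned with progressive disease and are not caught by the death exception is not in the documents; I assume 0 to 30%. I also assume that each of them truly progressed before 4 months and that there is no other censoring before then.

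**The plan's own figures reproduce.** Half-width: 1.645 × √(0.4 × 0.6 / 18) = 0.190. The Wilson lower limit is 0.104 at 4/18 and 0.142 at 5/18, so success needs 5 of 18. The exact probability of 5 or more is 0.906 at 40% (the plan states 90%) and 0.056 at 12%.

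**Effect of the rule on the estimate.** With r patients progression-free and k censored on day 1, the Kaplan-Meier rate at 4 months is r/(18 − k) instead of r/18. In expectation it is p/(1 − q):

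| q | true 12% | true 40% |
|---|---|---|
| 10% | 0.12/0.90 = 13.3% | 0.40/0.90 = 44.4% |
| 20% | 0.12/0.80 = 15.0% | 0.40/0.80 = 50.0% |
| 30% | 0.12/0.70 = 17.1% | 0.40/0.70 = 57.1% |

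**Effect on the false-success rate.** Sum over k the Binomial(18, q) probability of k, times the probability that a Binomial(18 − k, 0.12/(1 − q)) count reaches the smallest r whose lower limit exceeds 0.12. The limits, with S = r/(18 − k) and se = √(S(1 − S)/(18 − k)), are:

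- log-log: S raised to the power exp[1.645 se / (S |ln S|)]
- plain Greenwood: S − 1.645 se
- Wilson on the 18 − k remaining patients. This is for comparison only, since the SAP drops Wilson for this endpoint.

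| q | log-log | Wilson on remaining | plain Greenwood |
|---|---|---|---|
| 0 | 5.6% | 5.6% | 1.5% |
| 10% | 5.7% | 7.8% | 3.3% |
| 20% | 7.7% | 12.7% | 5.1% |
| 30% | 11.6% | 17.2% | 7.2% |

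**One data set.** Suppose 4 of 18 are progression-free, which is a failure when all 18 count (lower limit 0.104 Wilson, 0.087 log-log, 0.061 plain).

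| k | estimate | log-log | Wilson | plain |
|---|---|---|---|---|
| 3 | 4/15 = 26.7% | 0.105 | 0.126 | 0.079 |
| 4 | 4/14 = 28.6% | 0.113 | 0.135 | 0.087 |
| 5 | 4/13 = 30.8% | 0.122 | 0.146 | 0.097 |
| 6 | 4/12 = 33.3% | 0.132 | 0.159 | 0.109 |

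The conclusion reverses at k = 5 with log-log and at k = 3 with Wilson. With plain Greenwood it does not reverse up to k = 6. From 5 of 18, plain Greenwood goes from 0.104 (failure) to 0.122 (success) at k = 2.

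**Interval type.** With nobody censored, log-log needs 5 of 18 and keeps the 90.6% power. Plain Greenwood needs 6 of 18 and has 79.1%.

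**The case against.** Several points on the other side stand.

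- A reader might infer that the SAP records the same Group 2 patient as progressed for response and censored for PFS. It does not say so. The early-progressive presumption is written under Phase I response, and the Group 2 response sections (2.5.2.2 and 6.6.3.5) neither repeat nor cite it. The two rules collide directly in Phase I; for Group 2 the presumption arrives only by carry-over. The Group 2 bias does not need it, because it follows from SAP 2.4.2.2 alone.
- A reader might infer that the fastest progressors are lost as a class. Deaths up to the Cycle 4 scan are events, and SAP 6.6.6.1 intends to include deaths after discontinuation in overall survival. Those lost are alive at that time, or their deaths went unrecorded.
- A reader might take a constant hazard with 12% at 4 months, get 47% progressed by day 36 (1 − exp[(ln 0.12 / 4) × 36/30.4375]), and read this as the share affected. It is an assumed progression share, not the share never scanned.
- Scan-based progression is a defensible definition. SAP 2.5.1.3 says that symptomatic deterioration is not objective progression and asks for imaging even after discontinuation, which should shrink the unscanned group. Protocol 12.5 warns of pseudoprogression. Counting clinical calls will add some false events.
- The rule is stated openly, and SAP 6.6.1.2 requires counts of censoring reasons, so day-1 censoring will be visible.

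These points limit the size and the wording. None reverses the direction of the bias or supplies the missing sensitivity analysis.

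**Conclusion.** The concern holds in a limited form. SAP 2.4.2.2 removes from the Group 2 primary estimate any patient who leaves unscanned with progressive disease and is not caught by the death exception. That departs from the protocol's definition and from the stated inclusion of early leavers in SAP 6.6.1.2. Compared with counting these patients as failures, it can only raise the 4-month rate.

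The size depends on two things the documents do not give: the unscanned share and the interval type. At a share of 10% with log-log limits, the error rate barely moves (5.6% to 5.7%). At 30% it roughly doubles, to 11.6%. A reversed conclusion is possible but, with log-log limits and 4 of 18 progression-free, needs at least 5 unscanned progressors. The documents do not support the stronger inference that the primary result is bound to be badly inflated.

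This should be fixed. It is not a defect that by itself invalidates the analysis.

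**What to change.** In SAP 2.4.2.2, and so in 2.5.1.4 by reference:

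1. Count a patient with no post-baseline scan whose recorded reason for leaving is progressive disease as a PFS event. Date it when progression was recorded or withdrawal was decided, not at the last dose. The wording matters because SAP 5.1.1 takes the last-dose date from the End of Treatment page, and that date may precede the deterioration.
2. Restrict day-1 censoring to unscanned patients who left for other reasons, keeping the death exception.
3. State that the presumption in SAP 2.5.1.3 applies to Group 2.
4. Name the Kaplan-Meier interval type.
5. Pre-specify two sensitivity analyses: the present censoring rule, and the protocol's Wilson interval on all 18 FAS patients, with anyone lacking a 4-month progression-free assessment counted as a failure.

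Under the assumptions above, the first change returns the estimate to r/18 and the design to 5.6% error and 90.6% power with log-log limits.

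The cost is a few sentences and two tables. SAP 6.2 already draws the reason for ending treatment from the End of Treatment form. The PFS estimate becomes somewhat less favourable, and some clinical calls may not be true progression; the analysis under the present rule shows how much that matters.
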